9.3. Selection of Timing of Dose for Each Subject

Subjects will be randomized in a 1:1:1 ratio to trifarotene cream HE1 100 µg/g or 200 µg/g or vehicle cream. After Day 1, on which the study staff will apply the first administration of IP in the clinic, each subject will apply IP on up to 90% of their BSA twice weekly. It is suggested that each subject choose 2 specific days per week 3 to 4 days apart on which to apply their IP, and maintain that regimen each week throughout the study (Table 9-1). Visits for PK must occur at least 24 hours after the last application of the IP to avoid contamination of the blood samples with any IP that may have remained on the skin after the last application. Subjects whose treatment day falls on a scheduled study visit day should not apply the IP until after the visit. Subjects who participate in the PK substudy should have their Day 30 Visit scheduled on a treatment day, in which case the IP will be applied in the clinic on Day 30 after the predose PK blood draw. If the Day 30 Visit cannot be scheduled on a treatment day, the investigator should contact the medical monitor.

All subjects will be provided with diaries in which to record study drug application (days/times) and any areas of skin not treated (e.g., due to local reactions).

If a subject misses an IP application, they should apply the IP as soon as they remember and record the date/time in the subject diary. The next application should be 3 to 4 days apart, and subjects should continue according to their new regimen.

Subjects should not shower, bathe, or swim for at least 4 hours after IP application. No occlusive dressings should be used on areas to which IP is applied.

Subjects who continue into the OLE will receive trifarotene cream HE1 200 µg/g and apply it in the same manner as in the Double-blind Period for an additional 90 days.

Table 9-1: Sample Twice-weekly Dosing Schedule

	Week 1							Subsequent Weeks						
	Monday	Tuesday	Wednesday	Thursday	Friday	Saturday	Sunday	Monday	Tuesday	Wednesday	Thursday	Friday	Saturday	Sunday
Option 1	X			X				X			X			
Option 2		X			X				X			X		
Option 3			X			X				X			X	
Option 4				X			X				X			X
Option 5	X				X			X				X		
Option 6		X				X			X				X	
Option 7			X				X			X				X

9.4. Dose Adjustment Criteria

Local tolerance will be followed very carefully during the study. Subjects will receive information on study drug use and stopping rules and will be instructed to contact the site with any safety/tolerability issues. Study personnel will telephone subjects in between scheduled visits (i.e., at Day 7 and Day 45) to assess safety; an unscheduled clinic visit may be performed, if necessary. During all clinic visits, the investigator will assess local tolerability (stinging/burning, pruritus, or erythema on 0-3 scales [none, mild, moderate, severe]) for each treated body area (chest/abdomen, back, arms, legs, and face/neck), and the following procedures will be followed:

- If a score of 2 (moderate) is recorded for any of the local tolerability assessment scales (stinging/burning, pruritus, or erythema) on any treated area (e.g., the face), the study drug will be applied on this area only once weekly, until the score returns to <2. Continue to treat all other areas twice weekly provided the score is <2 on those areas.
- If a score of 3 (severe) is recorded for any of the local tolerability assessment scales (stinging/burning, pruritus, or erythema) on any treated area, the study drug will not be applied on that area until the score is back to <3 (i.e., “drug holiday”). Continue to treat all other areas twice weekly provided the score is <2 on those areas.

Any changes in dosing must be documented in the subject diary and the eCRF.

9.5. Treatment Compliance

Subjects will be asked to record their twice-weekly applications of IP in the diary during both the Double-blind Period and the OLE. Deviations from the planned doses (missed dose or timing) will be recorded on the subject’s eCRF. Study personnel will review diaries at each visit and diaries will be collected as source documents. Information from subject diaries will be transcribed on the appropriate eCRF pages for documentation of subject compliance with the IP.

Study personnel will assess treatment compliance with IP regimens by weighing kits (tubes and boxes, but not leaflets) before dispensing and upon return and by questioning the subject, at every postrandomization visit. At Baseline, the kit should be weighed before choosing the first tube for application by the study staff. A participant is compliant with study product if he or she takes at least 80% of the scheduled doses as assessed by diary entries, supplemented by amount of cream used derived from weighing the IP kits. A subject who is not compliant (for example, used 80-120% of IP tubes [which is more than what can be dispensed per tube at each application]) will be counseled at each visit on the importance of using the IP as instructed.

Subjects who taper to once-weekly application or who take a “drug holiday” for tolerability will not be reported as having deviated from the protocol (see Section 9.4 for dose adjustment and stopping rules); any changes in dosing must be documented in the subject diary and the eCRF.

9.6. Method of Assigning Subjects to Treatment Groups

In the double-blind, parallel-group, randomized period of the study, subjects who meet study entry criteria will be randomly assigned in a 1:1:1 ratio to trifarotene cream HE1 100 µg/g or 200 µg/g or vehicle cream. The randomization schedule will be computer generated using a permuted block algorithm and will randomly allocate IP to randomization numbers. The randomization numbers will be assigned sequentially through a central interactive web response system (IWRS) as subjects are entered into the study. Study center will not be a blocking factor in the randomization schedule.

Premier Research will prepare the randomization schedule before the start of the study. No one involved in the study performance will have access to the randomization schedule before the official unblinding of treatment assignments. No subject will be randomized into this study more than once.

In the OLE, all subjects will receive trifarotene cream HE1 200 µg/g.

9.7. Blinding and Unblinding Treatment Assignment

All subjects, investigators, and study personnel involved in the conduct of the Double-blind Period of the study, including data management, will be blinded to treatment assignment with the exception of a specified unblinded statistician and programmer from Premier Research who will have access to the randomization code. The statistician will have access to unblinded data if there is an unblinded DSMB review.

Study personnel will make every effort to safeguard the integrity of the study blind to minimize bias in the conduct of the study. Treatment unblinding is discouraged if knowledge of the treatment assignment will not materially change the planned management of a medical emergency. Unblinding will be permitted in a medical emergency that requires immediate knowledge of the subject's treatment assignment.

The investigator may discuss with the medical monitor in advance of unblinding a subject, if possible, if it is not deemed an emergency. However, the investigator has the ultimate decision for unblinding a subject for medical treatment and no procedures will prevent or delay necessary unblinding in an emergency for the subject's safety. For emergency unblinding, study personnel will use the IWRS code. If the investigator is not able to discuss treatment unblinding in advance, then he/she must notify the medical monitor as soon as possible about the unblinding incident without revealing the subject's treatment assignment.

The investigator or designee must record the date and reason for treatment unblinding on the appropriate eCRF for that subject. In all cases that are not emergencies, the investigator must discuss the event with the medical monitor prior to unblinding the subject's treatment assignment.

If treatment assignment is unblinded for an individual subject, study personnel will be notified of that subject's treatment assignment without unblinding the treatment assignments for the remaining subjects in the study. Thus, the overall study blind will not be compromised. If a subject's treatment assignment is unblinded, he/she may or may not be asked to withdraw from the study. The investigator will make this decision after consultation with the medical monitor.

The primary analysis period is the first 90 days of treatment (i.e., the Double-blind Period). Overall unblinding will take place at the end of the Double-blind Period of the study only after database lock has been achieved. A second analysis will take place for endpoints assessed from Day 90 through the OLE.

9.8. Permitted and Prohibited Therapies

All concomitant medications used (including over-the-counter medications and herbal supplements) will be recorded in the source document and on the appropriate eCRF.

Upon signing informed consent and entering the Screening Period, subjects may begin a Washout Period of up to 90 days. Participants will stop using physical and medical treatments for LI,

including balneotherapy, as well as the following prohibited medications, as applicable (Table 9-2).

Table 9-2: Washout Periods for Prohibited Medications^a

Medication	Washout Period
Topical Treatments	
Corticosteroids (except inhaled and ophthalmic corticoids)	2 weeks
Retinoids (e.g., tretinoin, tazarotene)	4 weeks
Vitamin D analogues	2 weeks
Immunosuppressants (e.g., tacrolimus)	2 weeks
Antracene derivatives, tar and salicylic preparations	2 weeks
Keratolytics (such as urea, lactic acid, propylene glycol, salicylic acid) except keratolytic shampoo	2 weeks
Systemic treatments	
Retinoids	8 weeks
Oral Vitamin A supplementation more than 3500 IU per day	2 weeks
Medication interfering with bone activity, e.g., corticosteroids, thyroid hormones unless the dose is stable and TSH is normal, cytotoxics, bisphosphonates, selective estrogen receptor modulators (SERM), teriparatide, calcitonins, tetracyclines, quinolones, thiazides, long-term salicylates, heparin, theophylline, barbiturates, colchicines. Vitamin D analogs taken at stable dose for at least 1 month are allowed)	8 weeks
QT-prolonging drugs	5 half lives
CYP Enzyme inducers (such as rifampicine, phenytoin, carbamazepine, phenobarbital, St. John's Wort)	3 months
CYP2C9 and 2C8 inhibitors (including, but not limited to the following: gemfibrozil, fluconazole, fluvoxamine, sulfaphenazole, miconazole, amiodarone, sertraline, sulfamethoxazole, valproic acid, voriconazole, trimethoprim, rosiglitazone, pioglitazone)	5 half lives
Monoclonal antibodies	5 half lives

^a Note: This list applies to both prescription and over-the-counter (OTC) medications

During washout, subjects may continue their standard of care of visible skin (face and scalp) for cosmetic reasons and of extremities (palms/soles) to avoid functional consequences on walking or moving their fingers. In the US/EU, this may include compounded emollients with keratolytics (alpha or beta hydroxyl acids) and/or urea. The investigator should approve and document these standard-of-care treatments in the eCRF. If the standard of care treatments of the face and/or palms/soles contain prohibited medications, they must be stopped at the Baseline Visit. Subjects may shower, but not bathe or swim. The IGA will be evaluated on the rest of the body at Baseline.

After completing any necessary washout of prohibited medications, subjects will return to the site to complete the study eligibility requirements.

9.8.1 Permitted Therapies

Subjects will be advised on permitted emollient(s) for use as often as needed on nontreatment days during the study; on treatment days, the use of emollient(s) is permitted except within 4 hours before or after study drug application. Similarly, protective sunscreen should be applied as often as needed, except within 4 hours before or after study drug application. Subjects may use their standard of care treatment on their faces and/or palms/soles after the Day 30 assessment if they

experience a worsening of IGA in those areas. In the US/EU, this may include compounded emollients with keratolytics (alpha or beta hydroxyl acids) and/or urea. These standard of care treatments should be approved by the investigator and documented in the eCRF.

Subjects who enter the OLE must stop standard of care treatment. If they experience a worsening of IGA they may use standard of care treatment on their faces and/or palms/soles after the Day 120 Visit if the standard of care does not contain prohibited medications. If those standard of care treatments include prohibited medications, the subject should be discontinued from the study.

Other concomitant medications are allowed (e.g., analgesics, antihistamines), but should be limited to those medications considered necessary. All concomitant medications, both prescribed and over-the-counter, should be recorded in the eCRF.

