9.8.2 Prohibited Therapies

The medications listed in [Table 9-2](#) are prohibited during the study. Balneotherapy is also prohibited during the Screening Period and during the study.

Subjects may not use concomitant keratolytics such as urea, salicylic acid, alpha, or beta hydroxyacids. Subjects may not use topical or systemic retinoids. Subjects may not take more than 3500 IU/day Vitamin A (e.g., as in a multivitamin). Use of benzoyl peroxide is permitted on nontreatment days for subjects with concomitant acne only); it must not be applied on treatment days due to risk of inactivation of trifarotene by benzoyl peroxide.

Subjects receiving excluded therapies will be ineligible for study enrollment or for continued treatment in the study, at the investigator's discretion with consultation with Mayne Pharma LLC and the medical monitor. For enrolled subjects who require prescription of a systemic azole, the principal investigator should discuss with the medical monitor whether the subject may continue in the study.

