13.1.4.1 Efficacy Endpoints

Primary efficacy endpoint: The proportion of subjects in each treatment group who experience successful resolution of LI where “success” is defined as clear/almost clear overall and at least a 2-grade change from Baseline at Day 90/EOT in the Double-blind Period on the 5-point IGA scale.

Secondary: The secondary endpoints are as follow:

- The difference in mean scores between the active trifarotene cream HE1 and vehicle groups in the following assessment indices from Baseline through Day 90:
 - 5-point VIIS scale for scaling
 - Individual score for roughness (Scale: 0–4)
 - Palm/sole Assessment (Scale: 0–4)
 - Quality of life per DLQI
- The difference in proportion of subjects with presence of fissures on palm/soles (presence/absence, number of fissures, and pain associated with fissures [on a 0-3 scale]) at Day 90 between the active trifarotene cream HE1 and vehicle groups

Exploratory: The exploratory endpoints are as follow:

- The difference in mean ectropion scores (ESS of 0–8) between the active trifarotene cream HE1 and vehicle groups from Baseline through Day 90
- The difference in quality of life per EQ-5D-5L scores between the active trifarotene cream HE1 and vehicle groups from Baseline through Day 90

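### Keratolytic standard of care on face and palms/soles in the Double-blind Period is permitted by Section 9.8.1 and prohibited by 9.8.2, and its trigger rests on an IGA that is not recorded for those areas

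*Protocol*

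**What the plan says.** Section 9.8.1, on the Double-blind Period, allows standard of care on two areas: "Subjects may use their standard of care treatment on their faces and/or palms/soles after the Day 30 assessment". The permission is conditional, and the section words the condition as "experience a worsening of IGA in those areas". On content it says that in the US/EU "this may include compounded emollients with keratolytics (alpha or beta hydroxyl acids) and/or urea". The investigator approves the use and it is documented in the eCRF.

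Section 9.8.2 says: "Subjects may not use concomitant keratolytics such as urea, salicylic acid, alpha, or beta hydroxyacids". It also bars all medications in Table 9-2 during the study, and that table lists topical keratolytics (keratolytic shampoo excepted). A subject on an excluded therapy is ineligible for continued treatment, subject to the investigator's judgment after consulting the sponsor and medical monitor. The section contains no exception for 9.8.1.

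Section 10.3.1.1 defines the IGA as one five-point grade and lists the areas left out. Palms and soles are on that list; the face is not. Section 9.8, after describing continued care of face, scalp and palms/soles during washout, says the Baseline IGA is scored on the remaining skin.

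Section 13.1.4.1 makes the Palm/sole Assessment a secondary endpoint, together with this one at Day 90: "The difference in proportion of subjects with presence of fissures on palm/soles". The provisions cited here read the same in the Amendment 2 and Amendment 3 texts in the file.

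**The concern.** Two consecutive sections give opposite instructions about the same agents, in the same period, on the same skin. The condition that is meant to decide who may use them refers to a score the study does not collect for those areas.

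Keratolytics and urea act on thickening and scale, which the palm/sole, fissure and IGA endpoints measure. If sites resolve the conflict differently, Day 60 and Day 90 values will include such use at some sites. At others the same clinical course will end in stopped treatment or a deviation. The Section 13.1.1 per-protocol population requires subjects to be free of significant deviations, so its membership would depend on which section a site happened to follow.

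**Working it through.** The plan gives no figure on this point, so the check sets the passages side by side.

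1. **Permission against prohibition.** Section 9.8.1 names keratolytics and urea among what may be used after Day 30 on face and palms/soles. Section 9.8.2 names urea and alpha and beta hydroxyacids among what may not be used, and bars Table 9-2 keratolytics as well. The agents overlap, the period overlaps, and neither section refers to the other. A subject who acts on 9.8.1 is by definition receiving an excluded therapy under 9.8.2.

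2. **Possible outcomes for one subject.** Take a subject with worse palms at Day 30 who restarts a urea cream. The site may (a) regard the use as permitted and continue, (b) stop study treatment under the 9.8.2 discretion, or (c) continue and record a deviation. Under (a) the Day 90 value stands and the subject can be in the per-protocol set. Under (b) later on-treatment data are lost. Under (c) the value stands but per-protocol membership is in doubt.

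3. **Trigger on palms and soles.** The trigger needs an IGA in those areas. Section 10.3.1.1 removes palms and soles from the IGA, so no palm/sole IGA exists to worsen.

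4. **Trigger on the face.** Table 2-1 schedules one IGA per clinic visit and no area-level IGA. The VIIS covers chest/abdomen, back, arms and legs. Roughness is scored on the skin overall. The face/neck entry in local tolerability records stinging/burning, pruritus and erythema, not scale. The ectropion score concerns the eye. No facial severity score is scheduled.

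5. **Face in the primary endpoint.** By the exclusion list in 10.3.1.1 the face counts. By the Section 9.8 sentence on the Baseline IGA it may not. The Baseline and Day 90 grades may therefore not cover the same skin.

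6. **Direction.** The inputs are the planning rates in Section 13.2: 70% active, 40% vehicle, difference 30 points. As an assumption for illustration only, let a share r of non-successes become successes through this care, with r from 5% to 20%.
   - Both arms equally: 30 × (1 − r) = 28.5 to 24 points.
   - Vehicle only: 30 − 60r = 27 to 18 points.
   - Active only: 30 + 30r = 31.5 to 36 points.

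   The difference shrinks or grows according to which arm uses the care. The protocol states neither the rate of use nor the arm. These lines show that the direction is open; they do not estimate an effect.

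**The case against.** The strongest defence is that 9.8.1 is a specific exception and 9.8.2 the general rule, so a sensible site would let the specific one govern. The drafting lends this some support, since 9.8.1 names the agents expressly. But 9.8.2 states no exception and attaches a consequence to use. The intended reading has to be guessed, and the unscorable trigger remains under either reading.

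A second defence is that handling of such use in the analysis belongs in the SAP, which is not at hand. That stands. The absence of a handling rule is not part of this point, and keeping observed values is a legitimate choice. An SAP cannot, however, repair conflicting instructions to sites.

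Three stronger readings are tempting and are not supported:

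- **Bias towards no effect.** A reader might infer that use follows worsening and so is commoner on vehicle. Section 5.3 lists scaling and dryness among reactions to the drug, so use could be higher on active. If 9.8.2 is enforced, the result is missing data or deviations, not dilution.
- **Further contradictions.** The Baseline rule, "If the standard of care treatments of the face and/or palms/soles contain prohibited medications, they must be stopped at the Baseline Visit", is compatible with a conditional restart after Day 30. The rule "If those standard of care treatments include prohibited medications, the subject should be discontinued from the study" applies to the OLE, a different period.
- **Biased palm/sole Baseline.** Withdrawal of care at Baseline applies to all arms alike, and the Section 13.1.4.3 model adjusts for the baseline score. It does not by itself bias the comparison between arms.

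The route to the primary endpoint is also thin. Facial care could change an IGA result only where the face alone kept an otherwise clear or almost clear subject from success.

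**Conclusion.** The text is wrong as written on two counts: Sections 9.8.1 and 9.8.2 contradict each other on keratolytics in the Double-blind Period, and the 9.8.1 trigger cannot be applied with the scores the study collects. Both rest on the protocol wording alone and need no assumption. The consequence is inconsistent conduct and an unstable per-protocol population, with possible distortion of the Day 90 palm/sole and fissure endpoints. Distortion of the IGA through the face is possible but less certain, because it is unclear whether the face is in the Baseline grade. No size or direction can be given. The point merits correction before database lock but does not by itself invalidate the primary analysis.

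**What to change.** 1. Reconcile 9.8.1 and 9.8.2 so that one rule covers the Double-blind Period, with an explicit cross-reference. Which rule stands is a clinical decision for the sponsor.
2. If a trigger is kept, express it on a scale scored on the area concerned. For palms/soles, the Palm/Sole Assessment is already recorded at each clinic visit. For the face, no separate severity score is scheduled, so the sponsor must say what is to be used. The threshold is likewise a clinical decision.
3. State whether the face is part of the IGA, in the same terms for Baseline and Day 90, and align Section 9.8 with 10.3.1.1.
4. Record start date and body area of such use in the eCRF, so that its effect can be examined in a sensitivity analysis.
5. State whether use under the reconciled rule counts as a deviation for the per-protocol population.

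The cost is one amendment, a site communication and two eCRF fields on use that is already documented. Use that began under the present wording would need to be classified before database lock.
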